4.2 Handling of dropouts or missing data

4.2.1 Strategy for handling missing data for efficacy analyses

Different approaches will be used to handle missing data including how the IE will be considered ([Section 3.4](#)).

In this section, 3 terms will be used to define binary and continuous endpoints:

- Non-composite binary endpoint: Binary endpoint derived based on one continuous measurement (eg, PASI90)
- Composite binary endpoint: Binary endpoint derived based on several continuous measurements (eg, ACR50)
- Composite continuous endpoint: Continuous endpoint derived based on several continuous measurements (eg, PASDAS).

Below is a table summarizing for all continuous endpoints (excluding composite continuous endpoints) observed ranges and whether they are represented by an integer value. These endpoints will be analyzed and/or used in the derivation of composite or non-composite endpoints:

Table 4-1: List of non-composite continuous efficacy endpoints

Efficacy endpoint	Minimum	Maximum	Integer value
BASDAI	0	10	
EQ-5D-3L dimension scores	1	3	Yes
EQ-5D-3L (VAS)	0	100	Yes
FACIT-Fatigue subscale score	0	52	
HAQ-DI	0	3	
hs-CRP	LLOQ/2 where LLOQ=0.10 mg/L	No maximum	
IGA	0	4	Yes
LDI	0	No maximum	
LEI	0	6	
mNAPSI	0	13	Yes
PASI	0	72	
PGA-Arthritis /PhGA-Arthritis	0	100	Yes
PGA-PsA / PhGA-PsA	0	100	Yes
PsAID-12	0	10	
PsAQoL	0	20	
PtAAP	0	100	Yes
SF-36 ^a			
Physical Functioning (PF)	19.26	57.54	
Role Physical (RP)	21.23	57.16	
Bodily Pain (BP)	21.68	62.00	
General Health (GH)	18.95	66.50	
Vitaly (VT)	22.89	70.42	
Social Functioning (SF)	17.23	57.34	
Role Emotional (RE)	14.39	56.17	
Mental Health (MH)	11.63	63.95	
Physical component summary (PCS)	5.02	79.78	
Mental component summary (MCS)	-3.33	80.09	
SPARCC	0	16	
Tender Dactylitis Count	0	20	Yes
TJC / SJC	0	68/66	
vdHmTSS	0	528	
Erosion score		320	
Joint space narrowing score		208	

Efficacy endpoint	Minimum	Maximum	Integer value
WPAI-SHP	0	100	

BASDAI=Bath Ankylosing Spondylitis Disease Activity Index; EQ-5D-3L=Euro-Quality of Life 5-Dimensions 3 Level version; FACIT=Functional Assessment of Chronic Illness Therapy; HAQ-DI=Health Assessment Questionnaire – Disability index; hs-CRP=High sensitivity C-reactive protein; IGA=Investigator Global Assessment; LDI=Leeds Dactylitis Index; LEI=Leeds Enthesitis Index; LLOQ=lower limit of quantification; mNAPSI=Modified Nail Psoriasis Severity Index; PASI=Psoriasis Area and Severity Index; PGA-Arthritis=Patient's Global Assessment of Arthritis; PGA-PsA=Patient's Global Assessment of Psoriatic Arthritis; PhGA-Arthritis=Physician's Global Assessment of Arthritis; PhGA-PsA=Physician's Global Assessment of Psoriatic Arthritis; PHQ-9=Patient Health Questionnaire-9; PSAID-12=Psoriatic Arthritis Impact of Disease-12; PsAQoL=Psoriatic Arthritis Quality of Life; PtAAP=Patient's Assessment of Arthritis Pain; SF-36=Short-Form 36-Item Health Survey; SJC= swollen joint count; SPARCC= Spondyloarthritis Research Consortium of Canada ; TJC=tender joint count; vdHmTSS=van der Heijde Modified Total Sharp Score; WPAI-SHP=Work Productivity and Activity Impairment Questionnaire – Specific Health Problem

^aminimum and maximum of the norm-based scores – Normal range for SF-36 scores is 0-100

4.2.1.1 Primary analysis of binary endpoints that are part of the testing hierarchy (primary and secondary endpoints)

All binary endpoints (composite & non-composite) are based on continuous component variables.

The primary analysis of binary efficacy endpoints that are part of the testing hierarchy is considered under an estimand framework in which missing data (due to study treatment discontinuation) is considered indicative of failed treatment and imputed to non-response. Further missing data for subjects on treatment, or data observed while not on treatment is also imputed to non-response.

This composite estimand approach to handling missing data which is the primary analysis method for binary efficacy endpoints is similar to the non-responder imputation (NRI) method.

4.2.1.2 Primary analysis of continuous endpoints that are part of the testing hierarchy (secondary endpoints)

For continuous efficacy endpoints that are part of the testing hierarchy, the primary analysis method is based on the hypothetical estimand approach as follows:

- If subjects have missing data regardless of whether the missing data is preceded by an IE, then missing data will be imputed based on the MI-Markov-Chain Monte Carlo (MI-MCMC) /Reference-Based imputation method ([Section 4.2.2.3](#)).
- If subjects have non missing data after IE, then such data will be set to missing prior to running MI.

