4.2.2.3 MI – MCMC/Reference-based imputation

For the primary analysis of the secondary continuous efficacy variables included in the testing hierarchy and the individual components of the ACR response, the referenced-based multiple imputation method will be used. In this imputation method, the missing data will be imputed based on data from the placebo group only (Mallinckrodt, 2013). This analysis will be performed only for the subjects randomized to Placebo and BKZ.

Reference-based MI assumes that the statistical behavior of the BKZ and placebo randomized subjects after discontinuing study medication becomes that of the placebo-treated subjects. All time points after study treatment discontinuation for BKZ and placebo groups will be considered missing. MIs are used to replace missing outcomes for BKZ and placebo-treated subjects who discontinued using multiple draws from the posterior predictive distribution estimated from the placebo arm.

Note : SAS 9.4 may be used for this analysis where equivalent steps to those outlined below will be used to perform the imputation.

In the case of continuous endpoints, the procedure will be implemented as follows on the raw values:

1. Data will be processed sequentially, one timepoint (visit) at a time, by repeatedly calling SAS® PROC MI to impute missing outcome data at visits t=1 (Baseline), ..., Week 16 (Week 16 being the time point of interest) using data from the placebo-treated subjects only.
 - a. Initialization. Set t=1 (Baseline visit). Create a dataset combining all records from BKZ and placebo subjects with columns for covariates (bone erosion and region) and outcome at Baseline. Impute missing values at Baseline using bone erosion at Baseline, and region. Note that both placebo and BKZ data will be used to estimate the imputation model.
 - b. *Iteration.* Set t=t+1. Create a dataset combining records from BKZ subjects with missing data at visit t and all placebo subjects with columns for covariates (bone erosion and region) and

outcomes at visits 1 to t. In this dataset, outcomes for all BKZ randomized subjects are missing at visit t and observed or previously imputed values at visits 1 to t-1. Outcomes for placebo-treated subjects are observed or missing at visit t or observed or previously imputed values at visits 1 to t-1. The outcomes should be sorted in chronological order in the model.

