- c. *Imputation.* Impute missing values for visit t using previous outcomes for visits 1 to t-1, bone erosion at Baseline, and region. Note that only placebo data will be used to estimate the imputation model since no outcome is available for BKZ-treated subjects at visit t. As a consequence, the input dataset should include all subjects from Placebo but only subjects from the BKZ arm that have values at timepoint t missing.
- d. Repeat steps 2a-2d for all timepoints after Baseline up to Week16, 100 times with different seed values (seeds ranging from 201 to 300) to create 100 imputed complete datasets. Subjects whose missing values were imputed in the last SAS® PROC MI call will be included in the input dataset for the next SAS® PROC MI call. Standard rounding rules will be applied to the imputed values. If the MI procedure yields a value outside of the pre-defined range for the given variable, the value will be updated to be within the predefined range of values for the endpoint of interest. For example, the imputed value for TJC will be updated to 0 or 68 in the case of an imputed value less than 0 or greater than 68, respectively.

2. The analysis will be done on the change from Baseline, and the model will be an ANCOVA model with treatment group, region, and bone erosion classification as fixed effects and the Baseline value as covariate.

For generation of summary statistics, the 100 imputed datasets will be combined, and simple means and standard errors will be calculated using Rubin's rules (via SAS® PROC MIANALYZE). For calculation of other descriptive statistics (median, Q1, Q3, minimum and maximum), Rubin's rules do not apply. MI estimates will be computed by calculating arithmetic means of the estimates from the multiple repetitions of the imputation algorithm. Thus, for median, Q1, Q3, minimum and maximum the following approach will apply:

- The data will be summarized by treatment, visit and imputation and the summary statistics will be computed.
- Results will be summarized by taking the mean value of each summary statistic at each visit across all imputations.
- The number of decimal places will remain the same as the original for display purposes (ie, if the mean was presented to 1 decimal place, the mean of the means will also be presented to 1 decimal place).

3. The results obtained from the 100 ANCOVA analyses in Step 4 (i.e. LSM for the treatment difference and the 95% CI for the contrasts) will be combined with Rubin's rules.

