8.2.2 Primary analysis of secondary efficacy variables

The secondary efficacy variables will be analyzed for all subjects in the RS by treatment group (except for vdHmTSS for which the analysis will be performed on the RAS).

As indicated in [Table 4–5](#), there are 8 secondary endpoints included in the testing hierarchy that will be tested in a chronological order until one is failed to be statistically significant.

For the other secondary endpoints (secondary endpoints which are not part of the testing hierarchy), the p-values produced by the statistical models will be considered nominal since these endpoints are not controlled for multiplicity.

For the secondary composite and non-composite binary endpoints, the same estimand structure (composite estimand) as the one defined for the primary efficacy analysis of the primary efficacy endpoint ([Section 8.1.2](#)) will be used. The NRI approach for handling missing data and the same analysis model will be considered, and the analysis results will be presented similarly, with the exceptions that the analyses performed on pooled data from PA0010 and PA0011 subjects will consider the region and the study-id factor as possible covariates for the modelling.

The statistical hypothesis for the binary variables at Week 16 is that the conditional odds ratio in the BKZ group compared with placebo treatment group is equal to 1.

For the secondary continuous endpoints, the analysis will evaluate the hypothetical estimand as defined below:

- Population = Subjects enrolled according to the protocol-specified inclusion/exclusion criteria and randomized to IMP.
- Subject level outcome = variable as stated in [Section 2.2.1.2](#)
- IE handling = An IE is defined as discontinuation of study treatment prior to Week 16. A hypothetical strategy for addressing IE will be implemented. This estimand targets the treatment difference in a scenario where withdrawal from study treatment does not occur, such that outcomes for subjects without an IE are as observed, and outcomes for subjects with an IE are treated as though they had completed treatment through Week 16 but on Placebo. A MI strategy will be used to impute any missing data and observed data after IE which will be set to missing prior to running MI. Such data will be imputed using reference-based MI, in which the MI model is based on data from the Placebo group.

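### For HAQ-DI and SF-36 PCS (and vdHmTSS outside the Week 24 exception), missing values of BKZ subjects with no intercurrent event are imputed from placebo, which neither the stated assumption nor the written estimand supports

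*SAP*

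**What the plan says.** Section 4.2.1.2 covers the primary analysis of continuous endpoints in the hierarchy: "If subjects have missing data regardless of whether the missing data is preceded by an IE, then missing data will be imputed" with the reference-based method of Section 4.2.2.3.

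Section 4.2.2.3 gives the rationale: "Reference-based MI assumes that the statistical behavior of the BKZ and placebo randomized subjects after discontinuing study medication becomes that of the placebo-treated subjects". The note to Table 4-2 says the same. At each post-Baseline visit, "Note that only placebo data will be used to estimate the imputation model since no outcome is available for BKZ-treated subjects at visit t". The model does use the subject's own history: "Impute missing values for visit t using previous outcomes for visits 1 to t-1, bone erosion at Baseline, and region".

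Section 8.2.2 defines the estimand. It first names the target: "This estimand targets the treatment difference in a scenario where withdrawal from study treatment does not occur". For one group of subjects the sentence then reads "such that outcomes for subjects without an IE are as observed". For the other group it provides that "outcomes for subjects with an IE are treated as though they had completed treatment through Week 16 but on Placebo". It then sends any missing value, as well as data observed after the intercurrent event (IE), to reference-based imputation. Section 8.1.4.4 puts two strategies for the ACR components under the same no-withdrawal description: (a) completion of treatment and (b) completion on placebo.

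Two provisions limit the reach of this. Section 8.2.1.5 uses MI-MCMC/monotone regression as primary for both vdHmTSS endpoints, for the Week 24 interim analysis only. Section 4.2.1.4 plans MI-MCMC/monotone regression, run separately by treatment group under Section 4.2.2.2, as supportive for the continuous hierarchy endpoints.

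**The concern.** The imputation rule is wider than its justification. Placebo-like behaviour is assumed after stopping study medication, but the rule also covers a BKZ subject who is still being dosed and has a gap. For that subject the estimand does not call for a placebo outcome, since it reserves that scenario for subjects with an IE. Estimator and estimand therefore differ for on-treatment gaps. Section 4.2.2.3 carries MCMC in its title, but its steps contain no within-arm step that would deal with such gaps.

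The label is a separate fault. A setting in which nobody withdraws and one in which withdrawn subjects finish "as though they had completed treatment through Week 16 but on Placebo" are different targets. A reader of the report could not tell which one the treatment difference estimates.

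What is at stake is the size and meaning of the reported differences for H2 and H4, and possibly for H6 and H9 at the Week 52/final rerun.

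**Working it through.** **Inputs (SAP Sections 2.3.1, 2.4.2 and 3.1).** 420 BKZ and 280 placebo subjects; two-sided alpha 0.05; Satterthwaite t-test.
- HAQ-DI: difference −0.24, SDs 0.47 and 0.50.
- SF-36 PCS: difference 5.83, SDs 7.38 and 9.51.
- vdHmTSS subgroup (H6): difference −0.30, SDs 0.72 and 0.71, in 45% of subjects, so 0.45 × 420 = 189 and 0.45 × 280 = 126.
- vdHmTSS overall (H9): difference 0.42, SDs 1.13 and 2.44.

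**The plan's own powers.** SE = √(s₁²/n₁ + s₂²/n₂), with power from the noncentral t distribution at difference/SE.
- HAQ-DI: SE = √(0.47²/420 + 0.50²/280) = 0.0377; power above 99.9% (stated >99%).
- PCS: SE = √(7.38²/420 + 9.51²/280) = 0.673; power above 99.9% (stated >99%).
- H6: SE = √(0.72²/189 + 0.71²/126) = 0.0821; power 95.4% (stated 95%).
- H9: SE = √(1.13²/420 + 2.44²/280) = 0.156; power 76.6% (stated 76%).

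All four reproduce.

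**Upper bound on the dilution.** Let m be the share of BKZ subjects with a missing Week 16 value and no IE. If each is imputed at the full placebo mean, the expected difference is (1 − m) × effect. The SAP gives no m, so 5% and 10% are assumptions. SEs are held at their planning values.

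| Endpoint | Planned | m = 5% | m = 10% | Power: planned / 5% / 10% |
|---|---|---|---|---|
| HAQ-DI (H2) | −0.24 | −0.228 | −0.216 | >99.9% throughout |
| SF-36 PCS (H4) | 5.83 | 5.54 | 5.25 | >99.9% throughout |
| vdHmTSS subgroup (H6)* | −0.30 | −0.285 | −0.270 | 95.4 / 93.3 / 90.6% |
| vdHmTSS overall (H9)* | 0.42 | 0.399 | 0.378 | 76.6 / 72.3 / 67.7% |

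*Only if reference-based imputation were used, which is not the case at Week 24.

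The largest shifts are 0.05 × 0.24 = 0.012 and 0.10 × 0.24 = 0.024 HAQ-DI units, and 0.05 × 5.83 = 0.29 and 0.10 × 5.83 = 0.58 PCS points.

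**Why the true loss is usually smaller for HAQ-DI.** The model conditions on earlier visits. The imputed Week 16 mean is the placebo mean plus the regression of Week 16 on the observed visits, applied to the BKZ-minus-placebo differences at those visits. I assumed 0, 40, 60, 80, 95 and 100% of the effect at Baseline and Weeks 2, 4, 8, 12 and 16, and visit correlations of 0.5 to 0.85 (exchangeable or AR(1)). A BKZ subject last seen at Week 12 then keeps about 46 to 81% of the effect, one last seen at Week 4 about 8 to 37%, and one with only Baseline none. PCS has only Week 4 between Baseline and Week 16 (Section 8.3.1.24), so less is retained there. vdHmTSS has no visit in between, so the bound is reached.

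**IE date.** Section 3.4 dates the IE at treatment end + 31 days. From Week 12 to Week 16 is 28 days, so a subject whose last dose was at Week 12 reaches Week 16 before the IE date. Having no IE is therefore not the same as still being dosed. The visit-number rule for missing visit dates in Section 4.2.2.2 is written under the binary endpoints and is not repeated for continuous ones.

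**The case against.** The choice is explicit. Section 4.2.1.2 deliberately covers both kinds of missing value, and Section 3.10 lists the move to reference-based imputation as a change from the protocol. It is conservative for a superiority claim, and it parallels Section 4.2.1.1, where missing binary data on treatment also count as non-response. The within-arm alternative and an observed-case analysis are already planned as supportive. For subjects with an IE, the estimator does what the placebo clause says. All of this stands, and it limits the point. It does not supply a reason for treating a dosed BKZ subject as a placebo subject, and it does not reconcile the two halves of the estimand sentence.

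A reader might infer that every continuous hierarchy endpoint is affected and that H6 and H9 lose power at the submission analysis. The SAP does not support that: Section 8.2.1.5 uses by-arm monotone regression for both at Week 24, which Section 4.3.1 names as the basis for the submission. The ±14-day film window likewise concerns vdHmTSS only.

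A reader might also infer that the remote visits in Section 5.2 will leave many HAQ-DI and SF-36 gaps. The examples there are joint, enthesitis, dactylitis and skin assessments and CRP; the two questionnaires are not named. For them the source of gaps is mainly missed visits or assessments.

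**Conclusion.** The point holds in limited form. For H2 and H4, the primary analysis imputes on-treatment gaps of BKZ subjects from placebo, against the method's stated assumption and the written estimand. For subjects with an IE the estimator matches the placebo clause, and the fault is the no-withdrawal label. It would go too far to say that the whole estimate misses its estimand.

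The bias is toward no effect and is bounded by the on-treatment missing share times the effect. The conclusions for H2 and H4 are not at risk: even at m = 15% with total loss of effect in those subjects, power for both remains above 99.9%. Type I error is not threatened.

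The H6 and H9 losses, from about 95% to 93 / 91% and from about 77% to 72 / 68%, arise only if reference-based imputation is used at the Week 52/final rerun. The SAP leaves this unclear. Section 8.2.1.5 confines its exception to Week 24, Sections 4.2.1.2, 4.2.2.3 and 8.2.2 do not mention it, and Table 4-4 calls the Week 52 secondary tables a rerun. Read literally, the primary vdHmTSS method changes between the two analyses.

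The sizes rest on assumed missing rates; the retained shares also rest on assumed correlations and an assumed response trajectory.

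**What to change.** 1. In Sections 4.2.1.2, 4.2.2.3 and 8.2.2, restrict reference-based imputation to visits after treatment discontinuation. Before that step, impute on-treatment gaps within the randomised arm by the method of Section 4.2.2.2.
2. State how the Section 3.4 date (treatment end + 31 days) classifies a missing Week 16 value, including when the visit has no date. Otherwise some subjects who have stopped could be imputed as if still on BKZ.
3. In Section 8.2.2 and strategy (b) of Section 8.1.4.4, drop the no-withdrawal description and say that outcomes after discontinuation are taken to follow the placebo arm.
4. Align Sections 4.2.1.2, 4.2.2.3, 8.2.1.5 and 8.2.2 so that the primary vdHmTSS method is the same at Week 24 and at the Week 52/final rerun.
5. If Week 24 results are already unblinded, correct the wording and report the split imputation as a sensitivity analysis.

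The cost is SAP wording plus one preliminary call to an imputation step already specified. The downside is a slightly less conservative primary estimate for on-treatment gaps.

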4.2.1.3 Supportive analyses of primary efficacy endpoint

For the primary endpoint (which is a composite binary endpoint) several supportive analyses assuming different missing data mechanisms will be conducted:

- The modified composite estimand approach: the IE is changed from all treatment discontinuation to treatment discontinuation due to AE or lack of efficacy. The same as the primary method will be used with the difference that only data after discontinuation due to AE or lack of efficacy is set to non-response. All other imputed data will be used.

- For the analysis of individual components of ACR, under the hypothetical estimand approach using the reference-based imputation methods ([Section 4.2.2.3](#)).
- The tipping point approach implemented within the MI framework, but only if the primary endpoint analysis result is statistically significant at alpha=0.05. ([Section 4.2.2.4](#)).
- The treatment policy strategy ([Section 4.2.2.5](#)).
- The observed case (OC) analysis that will only include observed data while on treatment. For subjects who had treatment discontinuation, only observed data up to treatment discontinuation date will be analyzed. For visits with missing data without treatment discontinuation, the data will remain missing. For observed data after treatment discontinuation, the corresponding visit data and subsequent visit data will be treated as missing.

4.2.1.4 Supportive analyses of endpoints that are part of the testing hierarchy (secondary endpoints)

The following supportive analysis methods will be performed for the secondary efficacy variables that are part of the testing hierarchy:

For binary endpoints:

- The modified composite estimand approach: the IE is changed from all treatment discontinuation to discontinuation of treatment due to AE or lack of efficacy. For composite or non-composite binary endpoints, the standard MI approach will be implemented (similarly as in [Section 4.2.1.3](#)) on the raw continuous score(s) (eg: PASI for the PASI90 endpoint) before deriving the binary endpoint based on the imputed score(s).
- The OC analysis.

For continuous endpoints:

- The hypothetical estimand approach:
 - If subjects have missing data regardless of whether the missing data is preceded by an IE, then missing data will be imputed based on the MI-MCMC/Monotone regression method ([Section 4.2.2.2](#)).
 - If subjects have non missing data after IE, then such data will be set to missing prior to running MI.
- The OC analysis.

4.2.1.5 Analyses of secondary endpoints that are not part of the testing hierarchy and other efficacy endpoints

The other efficacy endpoints and the secondary efficacy endpoints that are not part of the testing hierarchy will be analyzed as the secondary efficacy endpoints (with the exclusion of the MI-MCMC/referenced based imputation method for continuous variables) but with no designated priority.

For a combined binary endpoint based on the combination of a non-composite and a composite binary endpoint (as with the ACR50 and PASI90 combined endpoint), each binary endpoint will be derived independently, before deriving the combined endpoint.

